The available number of cases in each community is constrained by the local population and demographics as well as the pattern of hospital and emergencydepartment (ED) usage. Table 4 shows the projected number of cases in each community in three categories: total ED visits for chest pain; hospital discharges with ICD code 410 or 411; and confirmed cases of MI. Although the expected event rates in Table 4 come to 1202 per community for the 22-month trial, that rate is severely diminished by several mechanisms. First, a certain fraction of the patients discharged with 410/411 codes will present at the ED with complaints other than chest pain or will be admitted by some route not captured by the REACT sampling frame. Second, a certain fraction of cases will provide incomplete, invalid, or unusable data. Finally, a certain percentage of 410/411 diagnoses will fail to be validated. Early data showed that these mechanisms when compounded reduced the rate of usable cases by more than two-thirds, from 1202 to 375 per community. The REACT eligibility criteria were therefore revised to include all cardiac-related discharges. Broadening the criteria approximately doubled the expected sample, to 750 per community over 20 months, or a total of 15,000 usable cases.

The logistical demands of REACT measurement suggest, insofar as is compatible with sample-size requirements, that random subsampling of cases be conducted in the larger communities. Rather than lock the REACT design into a fixed subsampling scheme, the study will institute a conservative sampling plan that can be adjusted (without bias) as the data come in. In the smallest communities (two in the Washington field site and all four in the Texas site), 100% sampling will certainly be required throughout REACT. In the intermediate-sized communities, sampling will

begin at 100% but will be monitored by the Coordinating Center to determine whether "mid-course" adjustment to a smaller sampling fraction might be appropriate. In the largest communities (Worcester, MA and Eugene, OR), sampling will begin at 50% and will be similarly monitored and adjusted if necessary.

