REACT will follow the pattern employed in the analysis of the Minnesota Heart Health Program risk factor and morbidity and mortality data (97), and adapted for the joint analysis of data from the three major U.S. trials of community heart health promotion in the 1980's (71). Pre-intervention data from all 20 communities will be combined with postintervention data from the comparison communities to model a single secular trend. The intervention effect will then be estimated as a departure from that secular trend.

7. Subgroup analyses

Subgroup analyses are often desirable to provide insight into how and for whom an intervention achieved its effect. REACT plans a number of subgroup analyses, all secondary to the primary analyses. These include assessment of the treatment effect on delay among subgroups defined by sex, ethnicity/race, age, history of previous CHD, risk status, and other variables listed in Section IV. These analyses will be patterned after the primary analyses, with appropriate caution added to their interpretation.

8. Inferential parameters

All primary and secondary analyses will employ two-tailed tests with a nominal Type I error rate of 5%.

9. Intention to treat

A commonly followed principle in rigorously evaluated trials is the intention-totreat principle, which states that participants allocated to each condition must be retained in the primary analyses, even if that requires conservative procedures to estimate data for subjects lost to followup. REACT will be relatively protected in this regard, as it is not based on a cohort design and so will not be subject to the usual loss to followup problems. At the community level, the intention-to-treat principal implies that a community must be analyzed as belonging to the treatment condition to which it was randomized, regardless of how well the intervention was implemented (in the case of an intervention community) or how much the community may have been influenced by independent REACT-like messages (in the case of a control community).

B. Analytic Methods

1. Analysis of delay time in the primary population

The primary population for whom delay times in each community will be assessed consists of all patients with confirmed MI or unstable angina. This group will be referred to as *primary patients*. For the primary endpoint, delay time is defined to be the time between onset of symptoms and arrival at the hospital.

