An important subgroup of the primary population for whom we would like to assess the intervention effect is those patients with confirmed MI. Additional subgroups are defined by the individual level covariates \mathbf{x} (age, gender, and history of MI). Additional subgrouping variables are listed in Section IV. The primary analytic method will be carried out in each subgroup defined by these variables.

Differential intervention effects among subgroups will be tested using model (3), except that instead of $\beta + \lambda_i + Q_{j(i)} + \tau_k + V_{jk(i)}$, the coefficient in front of *t* will be $\beta + \lambda_i + Q_{j(i)} + \tau_k (1 + \mathbf{f}^T (\mathbf{x} - \overline{\mathbf{x}})) + V_{jk(i)}$. A significant value of a φ coefficient (using a two-tailed test at $\alpha = .05$) indicates a differential effect of intervention for different values of covariates. If this happens, the model will be used to compute estimates of the difference in slopes between intervention and control communities for the different subgroups defined by the covariate. The other covariates will be set to their average values.

5. Secondary endpoints

Several secondary analyses will attempt to assess the clinical consequences of decreased delay time. The hypotheses, discussed in Section X., are that reducing delay time will result in

- a. more frequent delivery of early revascularization;
- b. less severe disease;
- c. shorter hospitalization;
- d. lower mortality from MI and acute ischemia; and
- e. increased emergency department utilization (both appropriate and inappropriate).

Among the measures addressing these outcomes, many are proportions; for example,

a. proportion of primary patients who receive thrombolytic therapy or PTCA;

- b. proportion of primary patients who die in the hospital;
- c. proportion of primary patients who incur ventricular fibrillation within 24 hours of admission;
- d. proportion among ED patients with chest pain who turn out not to have MI or unstable angina.

For these dichotomous endpoints, the two-step procedure beginning with (4) will be used, with p denoting the probability of interest (for example, the probability that a patient will die in the hospital).

Other secondary questions are addressed by continuous measures; for example,

- a. average daily number of patients presenting in the emergency department with chest pain;
- b. average daily number of 911 calls for chest pain;

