At the individual level, if all sites are pooled, subsampling skews the ethnic composition of the overall REACT sample to some degree. These effects are detailed in Table 7. It should be emphasized, however, that a valid random subsampling scheme would not alter the ethnic balance of the sample collected in any given community. Since all primary and secondary REACT analyses, in keeping with the community randomization design, are planned at the community level, these would not be biased by subsampling.

B. Detectable effect, primary analysis

Sample size is essentially fixed in advance at both levels of REACT, on the community level at 10 pairs and at the individual level by the available number of cases or some convenient sampling fraction. The effect of the REACT Intervention in reducing delay time is by contrast difficult to predict, because comparable interventions have not previously been conducted. As a consequence, power calculations for REACT are most informatively framed with sample size, power, Type I error, and variance as fixed parameters (or, in sensitivity analysis, as independent variables) and detectable effect as the dependent variable. The requisite formulas are derived in this section. The results are tabulated and discussed in

Version 07/01/96

Section E. The sources and choices of operating parameters that enter into the formulas are detailed along with the mathematical derivation. A parameter summary is provided in Table 8.

The primary REACT endpoint is T, the delay time between onset of acute symptoms and arrival at the hospital. Because the distribution of T is skewed according to all reports from previous studies, the primary endpoint for analysis will be $y = \log_{10} T$. All other factors being equal, y will be assumed to have a normal distribution with mean μ and variance σ^2 . Thus T is log-normally distributed with median $M = 10^{\mu}$. In the log-normal distribution, approximately 95% of cases fall within a multiplicative range of $10^{\mu\pm 2\sigma}$. The multiplicative factor $R = 10^{2\sigma}$, according to pertinent data (Section II), is approximately 9. That is, 95% of delay times fall between 1/9 of the median value and 9 times the median value (Figure 7).

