Many of the secondary questions in REACT concern the primary endpoint as measured in populations, smaller or larger, that differ from the primary group of patients with confirmed MI or acute ischemia presenting with chest pain. Smaller groups of interest include the two sexes; ethnic subpopulations; and MI patients alone. Larger groups include all patients presenting at the ED with chest pain.

Two distinct questions may be formulated with respect to a subgroup: (1) Did REACT Intervention have an effect in that subgroup, considered alone? (2) Did REACT Intervention have a different effect in that subgroup compared with the complementary subgroup?

To calculate detectable effects in answer to the first question, it is necessary merely to increase or decrease the overall sample sizes in the calculation for the primary endpoint, in proportion to the size of the group. This assumes that all design and variance parameters are unaffected by moving to a larger or smaller group; for example, that inter-pair slope correlation (ρ) is the same for women as for the primary sample as a whole.

v CISIOII U //U1/90

To calculate detectable effects for a comparison between two complementary subgroups, the fraction f of each community to be compared to the complementary fraction (1-f) will be assumed the same in each community, although this is clearly not true for certain subgrouping factors such as ethnicity. The 20 community-level endpoints become 40, as slope can be measured separately in each subgroup in each community. The contrast of interest is a second-order difference in each community pair:

$$d' = \begin{bmatrix} b_{Subgroup \#1, Intervention} - b_{Subgroup \#1, Control} \end{bmatrix} - \begin{bmatrix} b_{Subgroup \#2, Intervention} - b_{Subgroup \#2, Control} \end{bmatrix}$$

The average contrast over all 10 pairs, $\overline{d'}$, is an unbiased estimate of the differential effect of REACT Intervention by subgroup. Its variance is

$$SE^{2}(\overline{d'}) = V(\overline{d'}) = \frac{4\sigma_{\beta}^{2}}{J}(1-\rho-\dot{\rho}^{*})$$
$$+ \frac{\sigma^{2}}{V,J^{2}} \sum_{j=1}^{J} \left[(fK_{j})_{Intervention}^{-1} + (fK_{j})_{Control}^{-1} + ((1-f)K_{j})_{Intervention}^{-1} + ((1-f)K_{j})_{Control}^{-1} \right]$$

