where $\rho + \rho^*$ is the correlation between two subgroup slopes drawn from the same community. ρ^* may be considered the *additional* correlation attributable to two slopes' coming from the same community, rather than merely from the same matched pair. It is reasonable that ρ^* should be at least as large as ρ . To be conservative we shall assume ρ^* equal to ρ .

The contrast $\overline{d'}$ serves to test the hypothesis of Intervention × Subgroup interaction. The detectable slope differential between complementary subgroups is

$$\Delta'\beta = SE(\overline{d'})(t_{\alpha/2} + t_{1-\Pi}).$$

In this case the t-statistic has 9 df.

D. Detectable Effect, Binary Endpoints

Many of the secondary endpoints of REACT are yes/no variables, such as receipt of thrombolytic therapy or use of 911 service. Accordingly the power analysis for secondary variables will be presented in terms of dichotomous outcomes.

A statistical model for binary endpoints can be formulated similarly to that presented above for the continuous, log-transformed primary endpoint. The prevalence of the binary endpoint at any point in time will be denoted p. To cover the wide range of binary endpoints of interest, the calculation has been performed for p=0.01, 0.05, 0.10, 0.20, 0.30, and 0.50. The numerical results are identical for the complementary cases p=0.99, 0.95, 0.90, 0.80, and 0.70.

The transformed prevalence y = logit(p) = ln[p/(1-p)] is assumed to follow an approximately linear time course:

$$y(t) = y(0) + \beta t$$
, $0 \le t \le 1.5$ yr.

The slope estimate b is again the community-level measure of interest. As derived from simple logistic regression, the variance of b is approximately $1/\pi(1-\pi)KV_t$, where π is the "average" prevalence over the time range (105).

The mean difference between Intervention and Control slopes has variance identical to the continuous case except for substitution of $1/\pi(1-\pi)$ for σ^2 . The random variance component σ_{β}^2 is related to the binary endpoint by $R_{\beta} = e^{2\sigma_{\beta}L}$, R_{β} being the Odds Ratio for the outcome in a community at the outer 95% limit of slope variation as compared to a community in the center of the slope distribution at the end of the *L*-year trial. The values $R_{\beta} = 1.05$ and 1.15 were used for sensitivity analysis as in the previous case.

The detectable slope difference,

$$\Delta\beta = SE(\overline{d})(t_{\alpha/2} + t_{1-\Pi}),$$

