Dothan (Houston Co.)	1100	1100 (100%)	550 (50%)	
Opelika (Lee Co.)	1247	1247 (100%)	623 (50%)	
Massachusetts				
Pittsfield/Dalton	726	726 (100%)	726 (100%)	
Westfield/W. Springfield	796	796 (100%)	796 (100%)	
Worcester	2578	1289 (50%)	645 (25%)	
Lowell	1406	1406 (100%)	703 (50%)	
Minnesota			(
Fargo/Moorheadd	1833	1833 (100%)	917 (50%)	
Sioux Falls	1650	1650 (100%)	825 (50%)	
Eau Claire	1650	1650 (100%)	825 (50%)	
LaCrosse	1467	1467 (100%)	733 (50%)	
Texas			(00,0)	
Brownsville	733	733 (100%)	733 (100%)	
Laredo	733	733 (100%)	733 (100%)	
Tyler	550	550 (100%)	550 (100%)	
Lake Charles	550	550 (100%)	550 (100%)	
Washington				
Shoreline	345	345 (100%)	345 (100%)	
Olympia	352	352 (100%)	352 (100%)	
W. Portland/Beaverton	1393	1393 (100%)	697 (50%)	
Eugene	2179	1090 (50%)	545 (25%)	
Total (22mo)	24,088	21,660	13,223	
Average per site	4808	4332	2645	
Avg per community	1202	1083	661	

Table 6. Expected Events, 22 months, and Subsampling Schemes

	Scheme A ("All")	Scheme B ("Biggest/2")	Scheme C ("Catch1000")
White	82.2	81.3	77.3
Black	7.5	8.0	8.2
Hispanic	8.5	8.7	12.6
Native American	0.5	0.5	0.5
Asian/Pacific Islander	2.5	2.5	2.3
Other	1.1	0.9	0.8

Table 7. Impact of Subsampling on Minority Representation

Table 8. Fixed Parameters and Parameter Values Used in Sensitivity Analysis

B Baseline period	0.333 yr
L Intervention period	1.5 yr
J Community pairs	10
R Residual 95% multiplicative range = $10^{2\sigma}$	9
End-trial variability factor due to random slope = $10^{2\sigma_{\beta}L}$	1.05, 1.15
Pair correlation of slope	0, 0.2, 0.4
* Intra-community, inter-subgroup correlation of slope	Equal to p
x Type I error (two-sided)	5%
I Power = 1 – [Type II error]	80%
Case mix in primary population	50% 410, 50% 411
Validation rate, 410 discharge	90%
Validation rate, 411 discharge	60%, 80%
Participation rate (response and good data)	85%
ED presentation with REACT-related symptoms	85% of 410/411
	discharges

	Subpopulation	Relative (%)	Absolute (min)		
	(%)		M=2.5 hr	M=3 hr	
	100	18	27	32	
Best case:	75	20	30	36	
$R_{\beta} = 1.05$	50	24	36	43	
ρ=0.4	40	27	40	48	
	30	30	45	54	
	20	35	53	64	
	10	46	69	83	
	5	58	87	105	
	1	86	129	154	
	100	20	29	35	
Worst case:	75	22	33	39	
$R_{\beta} = 1.15$	50	25	38	46	
ρ=0.0	40	28	41	50	
	30	31	46	55	
	20	36	54	65	
	10	46	70	83	
	5	58	88	105	
	1	88	129	154	

Table 9. Detectable Reduction in Delay Time, Secondary Populations*

*80% power, 5% Type I error (two-sided), K=600 per community.

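### The multiplicative φ test of effect modification loses most of its power when the average effect is small and is not the test Table 10 powers; separately, unweighted pair slopes are unworkable for unevenly spread race/ethnicity subgroups

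*Protocol*

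**What the plan says.** Section XI.B.4 gives two subgroup procedures.

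- **Within subgroups:** "The primary analytic method will be carried out in each subgroup defined by these variables". Section IV.G.1 includes race/ethnicity among the subgroup factors. The primary method (XI.B.1) is one slope per community, then an unweighted single-sample t-test on 10 pair differences. Inverse-variance weighting is described in XI.A.2 and XI.A.4 but is not among the steps adopted.
- **Between subgroups:** the intervention part of the slope in model (3) becomes τ_k(1 + φ′(x − x̄)), and a φ coefficient significant at two-tailed 0.05 "indicates a differential effect of intervention for different values of covariates". The vector x is gender, history of MI and age (XI.B.1).

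Appendix C, Section C powers a different statistic. The second-order contrast d′, averaged over pairs on 9 df, "serves to test the hypothesis of Intervention" × Subgroup interaction. It takes the subgroup fraction f as equal in every community, "although this is clearly not true for certain subgrouping factors such as ethnicity". Tables 9 and 10 rest on that framework; Table 9 is footnoted "80% power, 5% Type I error (two-sided), K=600 per community".

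**The concern.** Secondary aim 7 is the effect on delay by gender, age and race/ethnicity.

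Writing the interaction as a multiple of τ makes φ a ratio whose denominator is the average effect. If the intervention helps one group and harms or misses another, so that the average is near zero, the test has almost no chance of showing it. That is when the question matters most. Table 10 describes a different test, so the plan has no valid statement of the power of the analysis it specifies.

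For race/ethnicity the issue is separate. An unweighted mean of 10 pair differences gives a pair with two subgroup patients the same weight as one with hundreds, and no rule covers a community whose slope cannot be estimated.

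**Working it through.** **Inputs.** J = 10 pairs, 9 df. B = 0.333 yr, L = 1.5 yr, V_t = 0.237. The factor R, "according to pertinent data (Section II), is approximately 9", so σ = log10(9)/2 = 0.477. Best case: R_β = 1.05, so σ_β = log10(1.05)/(2 × 1.5) = 0.00706, with ρ = ρ* = 0.4. K = 600. Multiplier t(0.025) + t(0.20) = 2.262 + 0.883 = 3.146.

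**Reproducing the plan.**
- Table 9, full sample: SE² = 2(0.00706²)(0.6)/10 + 0.477² × 20/(0.237 × 100 × 600) = 0.000326, so SE = 0.0181. Detectable slope 3.146 × 0.0181 = 0.057 per year; reduction 1 − 10^(−1.5 × 0.0568) = 17.8% (stated 18%). At 40%, 5% and 1% subgroups: 26.5%, 58.1%, 85.7% (stated 27, 58, 86%).
- Table 10, 50/50: SE² = 4(0.00706²)(1 − 0.8)/10 + 0.477² × 10 × (4/300)/(0.237 × 100) = 0.00128, so SE = 0.0358. Detectable difference 0.113 per year, a 32% reduction (stated 32%).

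**The φ test.** Let γ = τφ be the additive interaction. With x centred, the estimates of τ and γ are almost uncorrelated (simulated r = 0.013). The delta method then gives

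z_φ = 1/√(1/z_γ² + 1/z_τ²) ≤ min(|z_γ|, |z_τ|).

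Example: z_γ = 4 and z_τ = 1 give z_φ = 0.97.

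Power with the interaction at Table 10's 0.113 per year. XI.B.4 gives no df for φ, so each range runs from the t critical value on 9 df (2.262) to the normal one (1.96):

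| Average effect τ (per year) | Wald test of φ | Additive contrast |
|---|---|---|
| 0.056 (planned detectable effect) | 36–58% | 81–88% |
| 0.035 | 11–24% | 81–88% |
| 0 | 0.3–1.3% | 81–88% |

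**Race/ethnicity.** Assume patient shares equal Table 1 population shares. Expected Black patients at K = 600 (share × 600):
- Brownsville 0.2%: 1.2
- Fargo/Moorhead 0.3%: 1.8
- Eau Claire 0.3%: 1.8
- La Crosse 0.5%: 3.0
- Sioux Falls 0.6%: 3.6

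If K instead follows Table 4, scaled by 750/1202, the five counts are about 0.9, 3.4, 3.1, 4.6 and 6.2. A slope needs at least two patients not all at time 0. With a Poisson mean of 1.2 that fails in 67% of cases; with 1.8, in 47%; with 3.0, in 21%.

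With these counts in the protocol's own variance formula, and Laredo's unreadable share set to 0.2%:
- Unweighted: SE = 0.201, detectable reduction 89%. Laredo at 1.0% to 0.1% gives 87–91%.
- Equal fractions at the mean share of about 9%, as Table 9 assumes: about 48%.
- Inverse-variance weights, SE = 1/√Σ(1/V_j) = 0.061: about 49% on 9 df.

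Section X.A says that broadened eligibility "approximately doubled the expected sample, to 750 per community over 20 months". At K = 750 the figures are 83–88% unweighted and 45% weighted.

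**The case against.** Several objections have force.

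- **The test type is not named.** For τ ≠ 0 the multiplicative form is a reparametrisation of the additive one, and a likelihood-ratio test of φ = 0 equals the additive test. A reader might infer that φ can never be more significant than τ. The protocol does not support that: the bound belongs to a Wald test with near-uncorrelated estimates and a common reference distribution. Still, a significant coefficient most naturally means a Wald test, and no choice of test identifies φ at τ = 0.
- **The protocol already discounts these analyses.** XI.A.7 makes them secondary and to be read with caution. Appendix C, Section E says power for subgroup differences is probably inadequate and that interactions of this size are unlikely. That stands, but the caution describes d′; the φ test is weaker still.
- **Not every subgroup procedure fails.** A reader might infer that both do. For large, evenly spread groups the within-subgroup method works: the 27% for women reproduces. Race is not in x, so the φ problem does not touch it.
- **The missing covariate-by-time term.** The model gives covariates no slope of their own, and one might infer bias. None is shown: a trend common to both arms largely cancels if case mix is similar.
- **The race counts are assumption-dependent.** They use population shares and an assumed Laredo value, and that pair supplies about 40% of the unweighted variance. The conclusion survives the ranges shown.

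**Conclusion.** The concern holds in two limited parts.

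1. The interaction test for gender, age and MI history is badly parametrised and does not match the contrast used for Table 10. Read as a Wald test, it has between under half and about two-thirds of the additive test's power when the average effect is as planned, and practically none when that effect is zero. The figures assume Table 10's best case and an interaction the protocol itself thinks unlikely. The dependence on τ does not rest on those choices.
2. For unevenly spread subgroups only, chiefly race/ethnicity, the unweighted 10-pair t-test is close to uninformative: about 87–91% detectable, with some slopes probably not estimable. Table 9's equal fractions understate this.

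Neither part affects the primary analysis.

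**What to change.** **Interaction.** In XI.B.4 replace the coefficient of t by β + λ_i + Q_j(i) + τ_k + V_jk(i) + (ψ + δ_k)′(x − x̄) and test δ, or use Appendix C's d′ on 9 df. Either is defined at τ = 0 and aligns the analysis with Table 10. Keep the caution that interaction power is low.

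**Race/ethnicity and other uneven subgroups.** Estimate the effect from one-stage model (3) fitted in the subgroup, or from inverse-variance-weighted pair differences, and say what happens when a community slope cannot be estimated.

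State the downside of weighting. For the Black subgroup the two Alabama pairs and Tyler/Lake Charles carry about 90% of the weight (24% + 26% + 39%), roughly 3.5 effective pairs, so the estimate mainly reflects those places. The 49% keeps 9 df; with about 2.5 df it is nearer 62%.

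**Cost.** One model line, a sentence or two, and a little programming. No new data.
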